2.4.5.2.2 Continuous endpoints anticipated to have a non-normal distribution

Continuous secondary efficacy endpoints defined in [Section 2.1.3.2](#), anticipated to have a non-normal distribution (eg, TG, TGRL and Lp(a)), will be analyzed using a robust regression model (ie, ROBUSTREG SAS procedure with M-estimation option) with treatment group as main effect, and randomization strata (as per IVRS) and corresponding baseline value(s) as covariate. The model for assessing the treatment effect by diabetes type will also include the treatment group-by-strata interaction. In case of non-convergence of the model, a model with less interaction coefficients will be fit. Missing values will be addressed using a multiple imputation model (see [Section 2.4.5.1.3](#)) that will at least include the same variables as used in the robust regression model (7). In the robust regression model, the analyzed endpoint at time point of interest will be derived from observed and imputed lipid values at this time point. The treatment group combined means will be provided with respective SE estimates. The combined mean difference between the treatment groups will be provided with the SE, 95% CI and p-value through the SAS MIANALYZE procedure. The analysis will be performed by diabetes type and on the pooled data.

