2.1.3.2 Secondary efficacy endpoint(s)

2.1.3.2.1 Key secondary efficacy endpoints

The key secondary endpoints are:

- Percent change in calculated LDL-C from baseline to Week 24, using all calculated LDL-C values during the efficacy treatment period (see Section 2.1.4, on-treatment estimand);
- Percent change in measured LDL-C from baseline to Week 24 (ITT estimand);
- Percent change in calculated LDL-C from baseline to Week 12 (ITT estimand);
- Percent change in measured LDL-C from baseline to Weeks 12 (ITT estimand);
- Percent change in non-HDL-C from baseline to Week 24 (ITT estimand);
- Percent change in Apo B from baseline to Week 24 (ITT estimand);
- Percent change in TC from baseline to Week 24 (ITT estimand);
- The proportion of patients reaching calculated LDL-C <70 mg/dL at Week 24 (on-treatment estimand);

- The proportion of patients reaching calculated LDL-C <50 mg/dL at Week 24 (on-treatment estimand);
- The proportion of patients reaching non-HDL-C <100 mg/dL at Week 24 (on-treatment estimand);
- The proportion of patients reaching non-HDL-C <80 mg/dL at Week 24 (on-treatment estimand);
- The percent change in Lp(a) from baseline to Week 24 (ITT estimand);
- The percent change in HDL-C from baseline to Week 24 (ITT estimand);
- The percent change in TG from baseline to Week 24 (ITT estimand);
- The percent change in LDL-C particle number from baseline to Week 24 (ITT estimand);
- The percent change in LDL-C particle size from baseline to Week 24 (ITT estimand).

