2.4.5.1.3 Sensitivity to handling of missing data

Sensitivity analyses will be conducted to assess the robustness of primary efficacy analysis with regards to handling of missing data (Section 2.5.3) (4). For all sensitivity analyses, outputs will be first described separately on the Type 1 diabetes patients and on the Type 2 diabetes patients, and then on the pooled data in ITT population. Forest plots will be also provided.

Multiple imputations:

In addition to the MMRM method, the multiple imputation method will be used to address missing values, in the randomized population, followed by the testing of treatment arms using an analysis of covariance (ANCOVA) model, with the intent to evaluate the robustness of the primary analysis using a different statistical method. Missing data from the randomized population will be imputed 100 times to generate 100 complete data sets, using the MI SAS procedure (using Markov Chain Monte Carlo). The percent change from baseline at Week 24 will be then derived from observed and imputed calculated LDL-C at this time point. The 100 complete data sets will be then analyzed using an ANCOVA model with treatment group and randomization strata (as per IVRS) as fixed effects, and the baseline calculated LDL-C value as continuous covariate, and the MIANALYZE procedure will be used to generate valid statistical inferences by combining results from the 100 analyses using Rubin's formulae (5, 6). The model for assessing the treatment effect by diabetes type will include an additional interaction: the treatment group-by-strata interaction.

The number of imputations (100) will be informally verified by replicating sets of 100 imputations and checking whether the combined results are stable. If not stable, the number of imputations will be increased and informally checked as above, and thus until stable estimates are obtained.

The imputation model will include:

- The variables included in the ANCOVA model, including the treatment group, the randomization strata (as per IVRS) and the baseline value. The model for assessing the treatment effect by diabetes type will include an additional interaction: the treatment group-by-strata interaction.
- The baseline characteristics such as: age, BMI, and gender. Age and BMI will be included as continuous variables.
- The calculated LDL-C values at Week 8, Week 12, Week 20 and Week 24 time points. Time points are those defined in Section 2.5.4.

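### The SAP treats TG, TGRL and Lp(a) as non-normal for analysis but sends their missing values to a normal-theory imputation written for LDL-C and states no scale; the cost is a small loss of precision, mainly for Lp(a)

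*SAP*

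**What the plan says.** SAP 2.4.5.2.2 groups the skewed lipids together and chooses a robust estimator for them: endpoints "anticipated to have a non-normal distribution (eg, TG, TGRL and Lp(a)), will be analyzed using a robust regression model", specifically the "ROBUSTREG SAS procedure with M-estimation option".

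For missing data, the same section says: "Missing values will be addressed using a multiple imputation model". It points to SAP 2.4.5.1.3 and adds only a minimum list of variables, a model "that will at least include the same variables as used in the robust regression model". Section 2.4.5.1.3 describes the sensitivity analysis for the primary endpoint, with missing values "imputed 100 times to generate 100 complete data sets, using the MI SAS procedure (using Markov Chain Monte Carlo"). Its model contains the calculated LDL-C values at each visit, treatment, stratum, baseline, age, BMI and gender.

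On the order of operations, 2.4.5.2.2 states that "the analyzed endpoint at time point of interest will be derived from observed and imputed lipid values at this time point". The concentration is therefore imputed first and the percent change computed afterwards.

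Two of the endpoints concerned are key secondaries in the fixed sequence of SAP 2.1.3.2.1: Lp(a) at Week 24 is 12th and TG at Week 24 is 14th, both under the ITT estimand. TGRL is an other efficacy endpoint (SAP 2.1.3.2.3). Protocol 11.4.2.2 left the imputation method to the SAP.

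**The concern.** The plan accepts skewness for the analysis but not for the imputation. MCMC in PROC MI draws from a multivariate normal distribution. On a skewed concentration, a single residual SD, set largely by patients with high values, is added to everyone's prediction. A patient with a low baseline can then receive a negative concentration, or a large positive one that becomes a change of several hundred percent once divided by that baseline.

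Missing values in these lipids are to be expected. ITT membership depends only on calculated LDL-C (SAP 2.3.1.1), so patients without a Week 24 Lp(a) or TG stay in and need imputation. TG also loses non-fasting samples and those of unknown fasting status (SAP 2.1.3). Lp(a) is drawn only at Weeks 0, 12 and 24 (Protocol 10), so little within-patient information supports the imputation.

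At stake is the precision of two steps in the hierarchy. SAP 2.4.5.2.4 also models raw TG, TGRL and Lp(a) values by time point after the same imputation, so negative concentrations would enter those reported means.

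**Working it through.** **1. Is a scale stated anywhere?** SAP 2.4.5.2.2 and 2.4.5.1.3 give none. SAP 2.5.2 only refers back to 2.4.5.2, and 2.5.7 is marked not applicable. SAP 2.5.1 has an LLOQ/2 rule for assay results below the quantification limit; it is not stated to cover imputed values. No passage requires the raw scale and none excludes a transformation. A programmer following the text literally would impute raw concentrations.

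**2. The plan's own figure.** There is none to reproduce: the documents show no SD, skewness or missing rate for these lipids, and the sample-size section is redacted. Everything below rests on assumptions.

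**3. Why Lp(a) is affected much more than TG.** Assume lognormal data with median m, log-SD s and log-scale correlation r between baseline and Week 24, with no treatment effect. On the raw scale:
- mean = m·exp(s²/2)
- SD = mean·√(exp(s²) − 1)
- correlation c = (exp(r·s²) − 1)/(exp(s²) − 1)
- residual SD = SD·√(1 − c²)
- prediction at baseline b = mean + c·(b − mean)

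| | Lp(a): m=20, s=1.2, r=0.95 | TG: m=150, s=0.45, r=0.65 |
|---|---|---|
| mean, SD (mg/dL) | 41.1, 73.7 | 166.0, 78.6 |
| c | 0.909 | 0.627 |
| residual SD | 30.7 | 61.3 |
| prediction at median baseline | 41.1 + 0.909·(20 − 41.1) = 21.9 | 166.0 + 0.627·(150 − 166.0) = 156.0 |
| P(imputed < 0) at median baseline | Φ(−21.9/30.7) = 0.24 | Φ(−156.0/61.3) = 0.005 |

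For an illustrative Lp(a) baseline of 5 mg/dL, the prediction is 8.3 and P(imputed < 0) = Φ(−8.3/30.7) = 0.39. A draw one SD above the prediction is 39.0, a change of (39.0 − 5)/5 = +680%. On the log scale the residual SD is 1.2·√(1 − 0.95²) = 0.375, so one SD multiplies the prediction by exp(0.375) = 1.45, and no draw can be negative.

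**4. Simulation.** Lognormal data, 2:1 allocation, Week 24 values missing completely at random. Assumptions: TG median 150, log-SD 0.35-0.45; TGRL median 28, log-SD 0.5; Lp(a) median 20-25, log-SD 0.9-1.2; within-patient correlation 0.60-0.70 for TG and TGRL and 0.90-0.95 for Lp(a); effects −10% for TG and TGRL and −22% for Lp(a). Normal-model imputation (20 draws) was run on the raw and log scales, followed by percent change, bisquare M-estimation and Rubin's rules, with 50-100 replicates per setting.

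| | Negative imputed values, raw scale | CI width raw/log, 5% missing | 10% missing | 20% missing |
|---|---|---|---|---|
| Lp(a), N=500 | 8-23% | 1.03 | 1.06-1.07 | 1.13-1.15 |
| TG, N=500 | 0.1-1.4% | 1.01 | 1.02-1.03 | 1.03-1.04 |
| TGRL, N=100 and 400 | 2-3% | 1.02 | 1.03 | 1.05-1.06 |
| Lp(a), N=100 | 17-20% | 1.02 | 1.05 | 1.13 |
| TG, N=100 | 1.4-1.6% | 1.01 | 1.03 | 1.05 |

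Log-scale imputation gave no negative values.

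**5. At 15% missing.** A separate simulation at Type 2 size gave Lp(a) SEs of 3.34 raw against 3.06 log, ratio 1.09, and TG SEs of 4.59 against 4.32, ratio 1.06. Its negative rates were 10-18% for Lp(a) and 2-3% for TG. A further one (N=400, Week 12 in the imputation model) gave about 14% negative Lp(a) values and Lp(a) SEs 3.5%, 6% and 10% larger at 5%, 10% and 15% missing. For TG it gave about 1% negative values and SEs 1-4% larger.

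**6. Estimates and power.** Mean treatment effects under raw and log imputation differed by at most about 0.4 percentage points. At N=500, Lp(a) power was 0.97-1.00 on either scale. TG power, at 10% missing with log-SD 0.45, was 0.82 raw against 0.87 log. Another run (80 replicates, 10% missing) gave, raw against log: at N=400, Lp(a) 1.00 and 1.00, TG 0.66 and 0.70; at N=100, Lp(a) 0.82 and 0.84, TG 0.21 and 0.23. With 60-80 replicates these gaps cannot be separated from simulation error.

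**The case against.** The strongest reply has five parts.

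- **The raw scale is inferred from silence.** Imputed lipid values could equally be back-transformed ones. This stands: a reader might infer that the SAP mandates raw-scale imputation, and it does not.
- **The pairing is deliberate.** SAP 2.4.5.2.2 cites a methodological paper whose title joins multiple imputation with robust regression. That supports the combination, but the SAP does not carry over any statement about scale.
- **M-estimation downweights extreme imputed values.** This stands, and is consistent with the nearly unchanged estimates. It does not make a negative concentration a valid value.
- **Missingness may be low.** Protocol 10.3.4 asks patients who stop treatment to attend all remaining visits. At 5% missing the cost is about 3% in interval width for Lp(a) and 1% for TG. This stands as a limit on size.
- **The simulations favour the fix.** With lognormal data, log-scale imputation is correct by construction. The LLOQ/2 rule puts a spike in the lower tail on the log scale: with an assumed Lp(a) LLOQ of 5 or 10 mg/dL, the penalty at 10% missing fell from about 6% to about 4% and 3%.

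A reader might also infer that two key secondaries are likely to fail, or that their estimates are biased. The checks support neither. Lp(a) power was close to 1 at the larger sample sizes on either scale, and the differences for TG were within noise.

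**Conclusion.** The gap is real: the text anticipates non-normality, refers the missing values to a normal-theory model built for another lipid, and gives neither scale nor bound. Followed as written, it would produce impossible values, in material numbers for Lp(a) and rarely for TG and TGRL. The consequence is a small, conservative loss of precision: for Lp(a) about 3% in interval width at 5% missing, 6-7% at 10% and 9-10% at 15%, and for TG about 1-6% over that range. At Type 1 size the Lp(a) figures are slightly lower, about 2% and 5% at 5% and 10% missing.

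These sizes depend on assumed lognormal distributions, assumed correlations and data missing completely at random; none of these comes from the documents. The primary endpoint is not affected. The point is worth settling because the remedy costs almost nothing and removes an analyst's choice from a confirmatory sequence before unblinding.

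**What to change.** Add to SAP 2.4.5.2.2 that TG and Lp(a), baseline and post-baseline values alike, are log-transformed for imputation (TRANSFORM statement with LOG in PROC MI) and back-transformed before the percent change is derived. Apply the same rule to the raw-value summaries in 2.4.5.2.4.

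TGRL needs its own rule, because it is a difference (total minus HDL minus LDL cholesterol, SAP 2.1.3) and can be non-positive even when observed. Either impute its components on the log scale and then subtract, or use a stated offset. Say how a non-positive result is handled, since subtraction can still give one.

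Keep treatment group and strata in the imputation model as 2.4.5.1.3 has them. Separate imputation by treatment group is not needed, and would leave about 100/3 ≈ 33 placebo patients in the Type 1 stratum.

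The cost is one SAP sentence, one program option and a small extra step for TGRL. The only statistical drawback found is the LLOQ/2 spike on the log scale, which reduces the gain somewhat.

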2.4.5.2.3 Binary endpoints

Binary secondary efficacy endpoints defined in [Section 2.1.3.2](#) (eg, proportion of patients below a threshold) will be analyzed using logistic regression with treatment group as main effect and corresponding baseline value(s) as covariate, stratified by randomization strata. Missing values will be addressed using a multiple imputation approach (see [Section 2.4.5.1.3](#)). The variables in the multiple imputation model will at least include the same variables as used in the logistic regression model. In the logistic regression model, the analyzed endpoint at time point of interest will be derived from observed and imputed lipid values at this time point. Treatment effects will be compared and the combined odds ratio estimate between the treatment groups, with their

corresponding 95% CIs and p-value will be provided via the SAS MIANALYZE procedure. The analysis will be performed by diabetes type and on the pooled data.

In the data dependent case that the logistic regression method is not applicable (eg, the response rate is zero in 1 treatment arm and thus the maximum likelihood estimate may not exist), the last observation carried forward (LOCF) approach would be used for handling of missing values and an exact conditional logistic regression would be performed to compare treatment effects. The LOCF imputation method will consist of using the last value obtained up to the Week 24 analysis window (or Week 12 as applicable) to impute the missing week 24 value (or Week 12 respectively).

In case of computing issues with exact logistic regression, the baseline level(s) will be entered in the model as a categorical variable(s) using quartiles. Exact odds ratio versus placebo, 95% CI, and p-value will be provided.

2.4.5.2.4 *Summary of results per time point*

Central laboratory values (in conventional (US) and international units), percent change from baseline and/or when appropriate absolute change from baseline (in conventional and international units) in calculated LDL-C, measured LDL-C, HDL-C, fasting TG, non-HDL-C, TC, ratio TC/HDL-C, Lp(a), Apo B, Apo A-1, ratio Apo B/Apo A-1, Apo C-III, TGRL, LDL-C particle size, LDL-C particle number will be provided at each time point for each treatment group in the ITT population using:

- For lipids other than TG, TGRL and Lp(a): LS mean and SE for each treatment group, obtained from the same MMRM models as used for endpoints above and including planned time points (see [Section 2.4.5.2.1](#)) and with raw values, changes from baseline, or percent change from baseline as response variable in the model as appropriate.
- For TG, TGRL and Lp(a): combined mean and SE for each treatment group obtained from multiple imputation approach followed by the robust regression models as used for endpoints above and including planned time points (see [Section 2.4.5.2.2](#)) and with raw values or percent changes from baseline as response variable in the model as appropriate.

All measurements, scheduled or unscheduled will be assigned to analysis windows (see [Section 2.5.4](#) on which value to select) in order to provide an assessment for these time points. Laboratory assessments other than the ones provided by the central laboratory will be excluded.

Summary tables and graphs over time of each parameter will be plotted by treatment group (LS mean + SEs by time point). The analysis will be performed by diabetes type and on the pooled data.

In addition, quantitative descriptive summaries by time point for each treatment group (value at visit and % change from baseline, or when appropriate absolute change from baseline) will be presented for all lipids using observed (ie, non-missing) data, and binary variables for LDL-C will be also provided in summary tables. These analyses will be performed by diabetes type and on the pooled data.

Calculated LDL-C will be described and plotted according to up-titration status. ie, according to whether the patients remained on the 75 mg dose or whether they were up-titrated to 150 mg.

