Continuous secondary efficacy endpoints defined in [Section 9.2](#), anticipated to have a nonnormal distribution (ie, TG and Lp[a]), will be analyzed using a robust regression model (ie, ROBUSTREG SAS procedure with M-estimation option) with treatment group as main effect and corresponding baseline value(s) as covariate. Missing values will be addressed using a multiple

imputation approach, which will be described in the SAP. The variables in the multiple imputation model will at least include the same variables as used in the robust regression model. The treatment group combined means will be provided with respective SE estimates. The combined mean difference between the treatment groups will be provided with the SE, 95% CI and p-value.

Binary endpoints

Binary secondary efficacy endpoints defined in [Section 9.2](#) will be analyzed using logistic regression with treatment group as main effect and corresponding baseline value(s) as covariate. Missing values will be addressed using a multiple imputation approach which will be described in the SAP. The variables in the multiple imputation model will at least include the same variables as used in the logistic regression model. Treatment effects will be compared and the combined odds ratio estimate between the treatment groups, with their corresponding 95% CIs and p-value will be provided.

In the data dependent case that the logistic regression method is not applicable (eg, the response rate is zero in 1 treatment arm and thus the maximum likelihood estimate may not exist), the Last Observation Carried Forward (LOCF) approach would be used for handling of missing values and an exact conditional logistic regression would be performed to compare treatment effects. The LOCF imputation method will consist of using the last value obtained up to the Week 24 analysis window (or Week 12 as applicable) to impute the missing week 24 value (or Week 12 respectively).

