2.3.1 Efficacy populations

The primary efficacy analysis population will be the ITT population.

2.3.1.1 *Intent-to-treat population*

The ITT population is defined as all randomized patients who have an evaluable primary efficacy endpoint defined as:

- Baseline calculated LDL-C value available;
- At least one calculated LDL-C value available within one of the analysis windows up to Week 24.

Patients in the ITT population will be analyzed according to the treatment group allocated by randomization (ie, as-randomized group).

This population will be used to assess the ITT estimands.

2.3.1.2 *Modified-intent-to-treat population*

The mITT population (otherwise referred to as the on-treatment population) is a subset of the ITT population defined as all randomized patients who took at least one dose or part of a dose of the double-blind IMP and have an evaluable primary efficacy endpoint during treatment period ie, Baseline calculated LDL-C value available;

- At least one calculated LDL-C value available during the efficacy treatment period and within one of the analysis windows up to Week 24.

The efficacy treatment period is defined as the time period from the first double-blind IMP injection up to 21 days after the last double-blind IMP injection.

Patients in the mITT population will be analyzed according to the treatment group allocated by randomization (ie, as-randomized group).

This population will be the basis for the on-treatment estimand evaluations.

2.3.2 *Safety population*

The safety population considered for safety analyses will be the randomized population who did actually receive at least one dose or part of a dose of the double-blind IMP.

Patients will be analyzed according to the treatment actually received.

The safety analysis will focus on the TEAE period defined as the time from the first double-blind dose to the last double-blind dose of IMP + 70 days (10 weeks).

In addition:

- Nonrandomized but treated patients or patients treated with the double-blind IMP before the randomization will not be part of the safety population, but their safety data will be presented separately;

- Randomized patients for whom it is unclear whether they took the study medication will be included in the safety population as randomized;
- For patients receiving more than 1 study treatment during the trial, the treatment group allocation for as-treated analysis will be the one to which the patient was treated with the longest duration.

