2.5.4 Windows for time points

Data analyzed by time point (including efficacy, laboratory safety data, vital signs, [REDACTED] ADA) will be summarized using the analysis windows given in [Table 2](#). These analysis windows will be applicable for all analyses, and they are defined to provide more homogeneous data for time point-specific analyses.

Table 2 - Analysis windows definition

Time point	Targeted study day	Analysis window in study days
Week 4	29	15 to 42
Week 8	57	43 to 70
Week 12	85	71 to minimum (98; study day corresponding to the first injection with IMP from kit allocated at up-titration IVRS contact)
Week 20	141	127 to 154
Week 24	169	155 to 182
Week 32	225	211 to 238

Study days are calculated from the day of first double-blind IMP, the day of first double-blind injection being Day 1. For randomized but not treated patients, Day 1 is the day of randomization.

If multiple valid values of a variable exist within an analysis window, the nearest from the targeted study day will be selected. If the difference is a tie, the value after the targeted study day will be used. If multiple valid values of a variable exist within a same day, then the first value of the day will be selected when time is available, else the scheduled visit will be selected.

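### Does the zero-responder fallback for binary endpoints (LOCF with exact logistic regression) need a defined trigger and a common missing-data rule across diabetes types?

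*SAP*

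**What the plan says.** By default, SAP 2.4.5.2.3 imputes missing lipid values, and "the analyzed endpoint at time point of interest will be derived from observed and imputed lipid values at this time point". Section 2.4.5.1.3, to which it refers, sets the number of imputations: "Missing data from the randomized population will be imputed 100 times to generate 100 complete data sets". Results are combined by Rubin's rules and reported for each diabetes type and pooled.

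The exception begins: "In the data dependent case that the logistic regression method is not applicable (eg, the response rate is zero in 1 treatment arm", with the reason that the maximum likelihood estimate may then not exist. In that case "the last observation carried forward (LOCF) approach would be used for handling of missing values and an exact conditional logistic regression would be performed". LOCF takes the last value up to the Week 24 window (or the Week 12 window). Protocol 11.4.2.2 has the same fallback: "the Last Observation Carried Forward (LOCF) approach would be used for handling of missing values", followed by the exact test.

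Four key secondary endpoints are binary and on-treatment, for example "The proportion of patients reaching calculated LDL-C <50 mg/dL at Week 24 (on-treatment estimand"). SAP 2.3.1.2 defines the efficacy treatment period as "the time period from the first double-blind IMP injection up to 21 days after the last double-blind IMP injection".

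**The concern.** Two things look loose.

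**Trigger.** The endpoint exists in 100 completed data sets, but the rule does not say whether zero is judged on the observed data, in any one set or in all of them. If the observed placebo arm has no responders and a few values are missing, some sets will contain a placebo responder and others will not. The choice of analysis could then appear to be made after seeing the data. The four binary endpoints are 8th to 11th of 16 in the fixed sequence, so a wrongly failed test would block the five that follow, if the sequence is applied within Type 1.

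**Comparability.** If the fallback fires in Type 1 alone, that odds ratio uses LOCF while Type 2 and pooled use imputation. The Week 12 window runs from day "71 to minimum (98; study day corresponding to the first injection with IMP from kit allocated at up-titration IVRS contact"), so a carried Week 8 or Week 12 value precedes any effect of 150 mg. Carrying it forward might understate the alirocumab response.

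**Working it through.** **Inputs.** SAP 1.1: about 500 patients, 2:1, given as 333 and 167; about 400 Type 2 and up to about 100 Type 1. SAP 2.4.5.1.3: 100 imputations. The documents give no placebo response rate and no missing-data rate, so those below are assumptions. All 2×2 results are unadjusted, whereas the planned models adjust for baseline.

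**Arm sizes.** 500 × 2/3 = 333.3 and 500/3 = 166.7, which reproduces the SAP. Type 1: 100 × 2/3 = 66.7 and 100/3 = 33.3, so about 67 and 33 at most. Type 2 placebo: 400/3 = 133.3.

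**Could it fire in Type 1 alone?** P(no responders) = (1−p)^n. The last column is (1−p)^33 × [1 − (1−p)^133].

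| Assumed placebo rate | Type 1, n = 33 | Type 2, n = 133 | Type 1 zero, Type 2 not |
|---|---|---|---|
| 2% | 51% | 6.8% | 48% |
| 3% | 37% | 1.7% | 36% |
| 5% | 18% | 0.1% | 18% |
| 10% | 3% | about 0% | 3% |

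So it could, at rates of a few percent. That is plausible mainly for a strict threshold such as LDL-C <50 mg/dL. It is much less so for <70 mg/dL: patients qualify on the Week −3 value, baseline is taken later, and SAP 2.1.1 includes a baseline category below 70.

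**Do the readings of the trigger differ?** Assume 0/30 observed placebo responders and 3 missing values, each imputed as a responder with probability q. The share of sets with at least one placebo responder is 1 − (1−q)^3.

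| q | Share of sets with a responder | P(no set is zero) = share^100 | P(all 100 sets zero) = (1 − share)^100 |
|---|---|---|---|
| 2% | 5.9% | below 1e-56 | 0.0023 |
| 5% | 14.3% | below 1e-56 | below 1e-6 |
| 10% | 27.1% | 2e-57 | below 1e-6 |

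An imputed set can have zero responders only if the observed data do. If the observed data do, at least one zero set is practically certain. Judging on observed data and judging on any set therefore coincide. Only the all-sets reading differs, and under it the fallback would almost never fire.

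**What happens under the all-sets reading?** Take 27/67 on alirocumab. Against 0/33, ordinary maximum likelihood stopped at a finite iteration gives a log odds ratio of 17.8 with SE about 1561. Against 1/33 it gives 3.07 with SE 1.05. Combining 100 sets by Rubin's rules:

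- one zero set: mean (17.8 + 99 × 3.07)/100 = 3.22, SE about 156, p about 0.98;
- 94 zero sets: p about 0.99;
- no zero set: p = 0.003.

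The first two p-values depend on the stopping rule (0.14 to 0.99 for 8 to 18 Newton iterations) but were never significant. A standard error in the hundreds or thousands is a plain sign that logistic regression is not applicable, which is the SAP's own criterion. The exact p for 27/67 versus 0/33 is 2.4e-6.

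**When does significance depend on the switch?** Fisher two-sided against 0/33: 7/67 gives 0.092, 8/67 gives 0.0498, 27/67 gives 2.4e-6 and 34/67 gives 4.2e-8. Only the first two straddle 0.05.

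**Size of an LOCF effect.** With 27/60 observed responders and 7 values missing, any imputation rule gives between 27 and 34 of 67. Exact median-unbiased odds ratios are 30.4 at 27/67 and 46.2 at 34/67, against 36.5 at the 30/67 expected under imputation. The range lies on both sides of that value, so it is a bound for any rule and says nothing about LOCF in particular.

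**Would a penalised-likelihood table help?** On identical data (27/67 versus 0/33), Firth's method (0.5 added to each cell) gives 27.5 × 33.5/(40.5 × 0.5) = 45.5, against 30.4 from the exact method. That difference between estimators is about as wide as the whole 30 to 46 range above, so the table could not isolate the missing-data assumption. It also loses power: p = 0.125 versus 0.0498 at 8/67, and 0.008 versus 2.4e-6 at 27/67.

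**The case for a change.** The best case for a change is that the all-sets reading is not excluded in writing. Read literally, it could report a failed test for a very large effect and stop the sequence before Lp(a), HDL-C, triglycerides and the two LDL particle endpoints. One sentence would settle it in advance. The LOCF definition also does not repeat the on-treatment restriction, and the missing-data sensitivity analyses in SAP 2.4.5.1.3 concern the primary endpoint only.

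Some of this stands. The trigger data set and the population in which it is judged are unstated. SAP 2.4.5.2.3 also does not say whether the by-type odds ratios come from separate fits, and firing in Type 1 alone requires that they do. But the criterion is written down, and an analyst facing an infinite estimate in even one set would apply the fallback. For on-treatment endpoints, SAP 2.1.3.2.1 already ties the estimand to values in the efficacy treatment period.

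The 150 mg argument is weaker than it looks. Patients with Week 8 LDL-C below 70 mg/dL stay on 75 mg, and a patient who stopped before Week 12 never received 150 mg. Protocol 10.3.4 also asks for an end-of-treatment sample within 5 days of stopping, if possible. For comparability, SAP 2.4.5.2.4 already plans observed-data summaries and LDL-C binary tables by diabetes type and pooled, though no binary tables for non-HDL-C.

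**Conclusion.** No change is needed. The open trigger is a gap that a competent analyst fills in one way: use the fallback whenever the estimate does not exist in the observed data or in any imputed set. The move to LOCF in a sparse arm is a fair trade-off. It is pre-specified in both documents and paired with a sound exact test. The obvious supplement, imputation with penalised likelihood, has lower power and is not like-for-like.

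What remains is limited. If the fallback fires in Type 1 alone, that odds ratio rests on a different missing-data assumption from Type 2 and pooled, and should be read that way. Significance would rarely change (only near 7 versus 8 of 67 in the unadjusted illustration), and the primary endpoint is untouched. This rests on assumed placebo rates of 2% to 10%, a few missing values per arm, Type 1 recruitment near its ceiling of 100, and separate fits by diabetes type.
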